With the goal of identifying treatment targets, we proposed a model of intermediate mechanisms linking anhedonia and smoking relapse.⁴ The model purports that when anhedonic individuals start smoking, pre-existing deficits in their ability to process and respond to natural rewards are alleviated because of nicotine is a reward-enhancer that increases the reinforcing properties of (and phasic dopamine bursts in response to) non-drug rewards.⁶³⁻⁶⁵ The nicotine bolus from each cigarette allows anhedonic smokers to experience temporary moments of pleasure and interest towards natural reward. Yet, when anhedonic smokers quit, pre-existing deficits in reward processing become unmasked and exacerbated by withdrawal-induced hyperdopaminergia, producing profound deficits in pleasure experience that motivate relapse back to smoking to re-attain nicotine-induced reward processing enhancement. Upon lapse, anhedonic smokers may derive greater nicotine reward from the lapse experience, which may in turn promote transition from lapse to relapse.

Empirical support for this model has accumulated in laboratory research supported in this grant's prior funding period (see C.1). Smokers with higher (vs. lower) anhedonia exhibit greater: (a) mood enhancement in response to natural rewards when given nicotine,⁶⁶ (b) abstinence-induced deficits in pleasure, positive mood, processing of reward-related stimuli,^{6,7,55} and (c) abstinence-induced increases in urge to smoke for pleasure.⁸ The association of anhedonia with lapse behavior is mediated by deficient positive mood.⁹ Thus, quit success among anhedonic smokers could be improved by treatments that ameliorate hypodopaminergia, improve reward processing, enhance positive mood, diminish urge, and block nicotine reward derived from smoking.

A.7 Rationale for Choosing Bupropion to Treat Anhedonic Smokers

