Bupropion targets the mechanisms underlying anhedonia's influence on relapse. Bupropion has demonstrable effects on boosts in positive mood, pleasure, cognitive processing of reward-related stimuli, and attenuation of smoking urge and behavioral signs of anhedonia during nicotine withdrawal.^{14,67,68} These effects appear to be mediated by bupropion's dopamine reuptake inhibition which enhances tonic and phasic striatal dopamine release.⁶⁸ Bupropion a nicotine acetylcholine receptor antagonist as well, and translational studies indicate bupropion's ability to block the rewarding effects of nicotine in animals and in humans,⁶⁹⁻⁷¹ Fatigue and amotivation, which co-occur with anhedonia, are improved by bupropion norepinephrine reuptake inhibition.⁷²

Bupropion is highly disseminable and efficacious. Bupropion at 300mg/day (BUP-300) is efficacious, safe, and tolerable.⁷² As one of the most widely prescribed medications in the US,⁷³ clinicians are often comfortable prescribing bupropion to a wide range of patients because it is available in a generic at a fairly low cost and has FDA approved indications for smoking, depression, and (in combination with naltrexone) obesity. Hence, new evidence supporting a novel application of bupropion would be readily adopted by the clinical community.

Specialized behavioral treatments have not been successful. We developed positive psychotherapy for smoking cessation—a novel intervention aimed to ameliorate pleasure by teaching skills to obtain pleasure through healthy means without resorting to smoking via several exercises (e.g., savoring pleasant experiences by being mindful and cultivating and prolonging the positive mood).⁷⁴ A pilot RCT showed that while it outperformed standard treatment in the overall sample, positive psychotherapy for smoking cessation did not improve quit outcomes relative to standard cessation counseling amongst anhedonic smokers.⁷⁴ Another treatment that promotes the identification of and engagement in pleasant activities—behavioral activation for smoking cessation—showed evidence of efficacy in a RCT, but did not affect anhedonia.⁷⁵ We suspect that because anhedonia is stable and heritable neurobehavioral phenotype,⁷⁶ pharmacological aids that correct underlying neurocircuitry may have a greater chance of producing a faster and more robust clinical response.

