Background. The first period supported a laboratory study of how 16 hours of abstinence diminishes reward processing, which in turn promote reinstatement of smoking on a laboratory analogue measure of relapse. The goal was to examine whether this risk pathway was disproportionately prominent in anhedonic smokers.

Addressing aims. By the end of the period, we successfully achieved the originally stated aims of this project. Two-hundred eighty-five participants completed the entire 3-visit study protocol, which more than doubled our a priori accrual recruitment goal of 128. Results showed that smokers with higher anhedonia exhibited greater abstinence-induced deficits in the non-drug reward processing and lapse behavior on several outcomes.

[name] et al. (2012). *Psychopharm*, 222(2), 343-351. Anhedonia predicts deficient processing of cues signaling social reward in nicotine abstinent but not nicotine sated states. Nicotine was predicted to offset pre-existing anhedonia-related reward processing deficits that were expected to become expressed and exacerbated during abstinence. We tested whether anhedonia predicted diminished cognitive processing of stimuli signaling social reward (happy facial expressions) in nicotine deprived but not nondeprived states using a novel task we previously developed (and intend to use in the proposed trial; see C.6). Results supported the conclusion that among anhedonic smokers, disrupted reward was offset when nicotine sated, but expressed and exacerbated upon abstinence, suggesting that treatments that alleviate reward processing deficits exacerbated in upon quitting may promote cessation in anhedonic smokers.

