Screening. After phone screen, an in-person screening will include both written and verbal informed consent, psychiatric interview, breath CO, urine pregnancy test, blood collection for labs, baseline assessments (C.6), and medical screening involving a physical exam. At the start of the baseline visit, the project team will explain the study and obtain written consent to participate. The study physician will review the medication with participants and obtain additional verbal consent to participate after reviewing the study treatment. Those ineligible will be provided referral information for psychiatric, addiction, family planning/OB (if appropriate) and smoking cessation (California quit line) resources. For participants who report past 30-day suicidal ideation, a suicide assessment screening protocol will involve a systematic assessment for emergent events, as well as referral to emergency mental health treatment and referral to a suicide prevention crisis hotline. In cases in which participants endorse current suicidality on the SCID-NP, [name] (or an available commensurately trained clinician if [name] is unavailable) will be called and will conduct a suicide risk assessment and protocol with the participant. If the participant appears at high risk and/or cannot contract for safety, emergency services will be called. To further monitor risk for suicide and/or self harm, study staff will review all questionnaire items that enquire about the presence of suicidal thoughts or ideations.

Randomization. Eligible participants will be randomized in a 1:1 ratio using urn randomization¹⁷⁸ for balance on sex, level of nicotine dependence (Fagerström Test for Nicotine Dependence; FTND),¹⁷⁹ BMI, and current anhedonia level (Snaith Hamilton Pleasure Capacity Scale; SHAPS)¹⁸⁰ across conditions.

Schedule. Participants will attend a pre-treatment visit involving eligibility screen and baseline measures (1-2 visits depending on physician availability), 7 in-treatment, and 3 post-treatment follow-up visits (C.6). On some visits subjects will complete supplemental measures of mediators (C.6). Certain visits will occur via phone if preferred by participant (Table).

Week	Pre-R**	-4	-2	-1	0	1	2	4	5-7	8	16	26
		Pre-quit Tx			Post-quit Tx					Post-tx F/U		
Counseling		X	X	X*	X	X*	X*	X				
Medical visit/labs	X***	X								X***		
Medication		X	X	X	X	X	X	X			X	
Core Ax		X	X	X	X	X	X	X				
Supplemental Ax		X	X		X			X				
Outcome Ax	X						X			X	X	X

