Outcome assessments (Baseline, 4-wk, 8-wk, 16-wk, 26-wk). Primary outcome: Point prevalence abstinence (PPA) self-report of no smoking or use of any other tobacco products (including e-cigarettes) in past 7-days (not even a puff) verified by salivary cotinine ≤ 10 ng/ml is our primary outcome. Secondary outcomes: (a) Smoking cessation milestones derived from Smoking Timeline Follow Back interview (i.e., achieving ≥ 24 hr abstinence, days to lapse, days from lapse to relapse; C.7), (b) The 29-item Inventory of Depressive and Anxious Symptomatology¹⁹⁶ Social Anxiety, General Depression, Traumatic Intrusions subscales; (c) 18-item Adult Self-Report Scale for ADHD¹⁹⁷ adapted for past-week symptom assessment; (d) SHAPS anhedonia scale,¹⁸⁰ (e) objective body weight via a medical-grade scale; (d) adiposity via bioimpedance monitor (InBody520, GE Healthcare)—a non-invasive 2-min scan that analyzes body electrolytes to yield fat, muscle, and water composition estimates, which we will use to generate percent body fat outcomes. In addition to self-reports of medication adherence, detectable bupropion, >5 ng/mL in urine¹⁹⁸ during study visits will be used as a supplemental marker. Though participants will be told to avoid use of other quit treatments, e-cigarettes, or tobacco/nicotine

products during the trial, these will still be assessed via self-report and participants who report transitioning to e-cigarettes will be analyzed as an exploratory intermediate outcome.

C.7 Analytic Plan

Preliminary Analyses. Distributions will be examined to determine the need for normalizing transformations. Using ANOVA or X^2 test, we will examine if groups differ at pretreatment on relevant variables (despite randomization) to inform possible inclusion in analyses.

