Primary Aim 1: Smoking Outcome. 7-Day biochemically-verified PPA (missing coded as smoking) at 4- 8- 16- and 26-week post-quit follow-up will be evaluated using individual latent growth curve models (LGCM) for longitudinal binary outcomes including planned covariates (FTND, sex, SHAPS anhedonia score, BMI), the main effects of medication (BUP-450 vs. BUP-300), and the effect of time. Non-linear effects of time will be explored using nested likelihood ratio tests prior to evaluating hypotheses. Treatment by time interactions will be examined to characterize medication effects before and after treatment termination. To understand at what stage of the cessation process the treatments exert their effects, we will also analyze cessation milestone outcomes of attaining abstinence (yes vs. no abstinent for >24hr in the first 2 weeks post-quit), days to lapse (i.e., first puff), and days from lapse to relapse (i.e., first puff until the onset of 7 consecutive days of smoking) using logistic and cox regression. Sensitivity analyses of treatment effects will examine medication adherence and counseling visit attendance as moderator of treatment effects and we will re-analyze primary models in the subset of fully-adherent participants. Additional comparisons of side effects between the conditions will be conducted to verify tolerability of BUP-450.

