Primary Aim 2: Mediation. Aim 2 will examine slopes from individual piece-wise LGCMs (or raw difference scores when only 2 timepoints available) to model changes in reward processing (see C.6) prior to quit day, the jump from pre to 1-week post-quit, and post-quit changes. A latent variable framework using Mplus 7.4 will allow estimates of treatments on individual growth in mediators (path 'a') to be modeled jointly with effects of growth in likelihood of abstinence (path 'b') using models that limit bias in estimates and provide accurate evaluation of mediation using bias corrected effect estimation and product of coefficients procedures. We will attempt to create a composite that amalgamates all reward processing mediators using principal component analysis (PCA), or if a strong component is not detected, test each raw variable individually. We will model time to lapse first and other smoking outcomes secondarily with and without smoking as a time-vary covariate. Additional multiple mediator models adding all 3 growth pieces simultaneously and including the discriminant constructs (negative affect, urge to smoke to alleviate negative affect) will be test the specificity of effects.

Secondary Aims: Aim 3 will examine medication effects on anhedonia (SHAPS) and related psychopathology (i.e., depressive, social anxiety, ADHD, PTSD symptoms) and body weight and body fat percentage trajectories using individual growth models (intercept and slope) of assessments at visits during treatment. Moderation of the differential effect of treatment (Aim 4) will be assessed with interaction terms of treatment condition and corresponding moderators (SHAPS, depressive, social anxiety, ADHD, PTSD symptoms) in successive models as described above in LGCM.

Supplemental analyses of the biological variable of sex and other characteristics (age, ethnicity/race). Using the strategies above, we will examine if sex, ethnicity/race, and FTND moderate treatment effects on primary and secondary outcomes. We will report sex-stratified analyses and test, amongst women, whether days since menstruation at the onset of treatment and quit day moderates outcome using several classification methods (follicular vs. luteal; early follicular vs. late follicular vs. mid luteal vs. other).

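### Aim 2 relates mediator pieces built on post-quit readings to time to first puff without requiring the reading to precede the lapse, so path b for those pieces is open to reverse causation of uncertain direction

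*Combined protocol and SAP*

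**What the plan says.** Section C.7 (Primary Aim 2) models change in reward processing in three pieces: "prior to quit day, the jump from pre to 1-week post-quit, and post-quit changes". Arm effects on these pieces are path a; their relation to smoking outcomes is path b. On outcomes it says: "We will model time to lapse first and other smoking outcomes secondarily with and without smoking as a time-vary covariate". Under Primary Aim 1 the lapse outcome is "days to lapse (i.e., first puff").

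Hyp 2 in the Specific Aims needs a sequence: dose changes reward processing, and that change then affects abstinence. Lapse can be dated, because section C.6 lists "Smoking cessation milestones derived from Smoking Timeline Follow Back interview" among the secondary outcomes and gives the timeline follow-back at all in-treatment visits.

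C.7 states no lag, landmark or lapse-free condition for mediator readings. Its references to limiting bias and to bias-corrected estimation concern estimation, not time order.

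**The concern.** A first puff can come before the week-1 reading or any later one. For anyone in that position, the jump or post-quit piece contains a reading taken after the event it is meant to explain. If lapsing changes the score, path b partly measures the effect of lapse on reward processing.

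The protocol gives reasons for a shift in either direction:

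- **Lapse raises the score (pushes path b against Hyp 2).** Section A.6: "The nicotine bolus from each cigarette allows anhedonic smokers to experience temporary moments of pleasure and interest towards natural reward". Section C.1: "disrupted reward was offset when nicotine sated, but expressed and exacerbated upon abstinence".
- **Lapse lowers the score relative to abstainers (pushes path b towards Hyp 2).** Section A.9 says that mental health gets better in people who stay quit.
- **The shift may be small or may differ by arm.** A.6 describes the nicotine effect as short-lived, and section A.7 credits bupropion with an ability to "block the rewarding effects of nicotine in animals and in humans".

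A supportive, null or wrong-signed path b for a post-quit piece could therefore not be read as the effect of reward processing on lapse.

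**Working it through.** **1. The plan's own figure.** C.8 gives mediation power above 0.81 at N = 375, with d above 0.3 for path a and above 0.17 for path b.
- Sample: 300/(1 − 0.20) = 375.
- Path a: Φ(0.30 × √(375/4) − 1.96) = Φ(0.945) = 0.83.
- Path b, with 0.17 as a standardized coefficient: Φ(0.17 × √375 − 1.96) = 0.91. With 0.17 as a two-group d: 0.38.
- Products: 0.83 × 0.91 = 0.75, or 0.83 × 0.38 = 0.31.

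The simulation model behind 0.81 is not given, so that figure cannot be reproduced. The ordering point does not depend on it.

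**2. Time order by piece.**

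| Piece | Last reading | Can a first puff come earlier? |
|---|---|---|
| Pre-quit | By quit day | No |
| Jump | 1 week post-quit | Yes |
| Post-quit change | After week 1 | Yes |

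**3. How many are exposed.** C.8 plans week-4 abstinence of 45% and 30%, with 150 per arm.
- Non-abstinent at week 4: 150 × 0.55 + 150 × 0.70 = 187.5, or 62.5% of 300.
- If the 20% attrition is already coded as smoking: (187.5 − 60)/(300 − 60) = 53% of those observed.
- Lapsed by week 1, with a constant hazard through the week-4 rates (assumed): 1 − 0.45^(1/4) = 18% and 1 − 0.30^(1/4) = 26%, mean 22%. With early-weighted lapses (Weibull shape 0.5, assumed): 1 − 0.45^(1/2) = 33% and 1 − 0.30^(1/2) = 45%, mean 39%.

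Point prevalence is only a proxy for lapse, since people can lapse and recover.

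**4. Illustration with no true path b.** Assumed: N = 300, reading SD about 1, within-person correlation 0.5, arm effect 0.3 SD, constant hazard, every lapse shifting later readings, Cox model with arm, 1,000 runs. Entries are the percentage of runs with path b significant.

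| Shift after lapse | Pre-quit | Jump | Post-quit |
|---|---|---|---|
| None | 4.1 | 4.4 | 6.1 |
| −0.3 SD | 5.4 | 19 (HR 0.94) | 16 (HR 0.95) |
| +0.3 SD | 5.0 | 18 (HR 1.06) | 15 (HR 1.05) |

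**5. Illustration with a true log HR of −0.17 per SD.** Entries are the mean path b at a +0.3 SD shift, for constant-hazard / early-weighted lapses.

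| Piece | All lapsers shifted | Half shifted |
|---|---|---|
| Jump to week 1 | −0.11 / −0.07 | −0.14 / −0.12 |
| Week 1 to 4 | −0.12 / −0.15 | −0.15 / −0.16 |
| Week 0 to 4, if week 4 is the only post-quit reading | −0.06 / −0.05 | −0.12 / −0.11 |

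A −0.3 SD shift takes the week 0 to 4 estimate to −0.28 to −0.29 (all) or −0.22 to −0.23 (half). With no true path b, that shift gives both paths significant in 39–43% (all) or 12–13% (half) of runs, against 2% with no shift.

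**6. Smoking as a covariate.** In a first-puff model nobody still at risk has smoked since quit day, so the covariate is constant among them. Adjusting the mediator for smoking instead held false positives at 2.2–4.5% in step 4, where the shift is additive and equal in both arms. In a simple stand-in for the joint model with no shift, the same kind of adjustment cut a true path b of −0.17 to about −0.05.

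**7. Restricting to participants lapse-free at week 4.** 150 × 0.45 + 150 × 0.30 = 112.5 remain. Path b is recovered (−0.17) with 33–41% power. Path a falls from 0.30 to about 0.24 SD, because arm and mediator both affect who remains. Power for both paths is about 7–10% (about 13% at a log HR of −0.31), against about 61% with everyone and no shift.

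**8. Using a later outcome.** With week-8 abstinence regressed on week 0 to 4 change and no true effect, a −0.3 SD shift in all lapsers gave 15–34% rejection unadjusted. Adjusting for smoking at week 4 gave 4.2–4.9% across all shifts tried.

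**The case against.** The strongest reply has four parts.

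**Hyp 2 is about odds of abstinence.** Abstinence at weeks 8 to 26 follows a week-1 or week-4 reading. That is right and limits the strict ordering fault to time to lapse, but time to lapse is the outcome modelled first. Step 8 shows that later abstinence also needs adjustment for smoking at the reading.

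**The plan already runs models with smoking as a covariate.** This is a partial safeguard: it can remove a simple additive shift equal in both arms. It sets no order, may fail if the lapse effect differs by dose, and neither version is named as deciding.

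**The sizes are assumed.** This stands in full. The shift, the share carrying it, the correlation and the lapse curves are not in the documents; latent slopes were not simulated; and 0.17 is a lower bound. Reading it as a log HR of −0.31 (0.17 × π/√3) makes the loss proportionally smaller.

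**A landmark analysis is a poor remedy for mediation.** This also stands. It selects on a post-randomization event, and step 7 shows the loss.

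A reader might also infer from the schedule table in C.5 that no week-1 mediator reading exists, since the table as extracted marks supplemental assessments only at weeks −4, −2, 0 and 4. The documents do not support that. The prose says only "On some visits subjects will complete supplemental measures of mediators (C.6"), C.7 relies on a week-1 value, and other rows look displaced in extraction: outcome assessment is marked under week 2 where C.6 says week 4.

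**Conclusion.** The ordering rule is missing, and the gap matters for the jump and post-quit pieces when the outcome is time to first puff. Confidence is high on the gap and low on the size of the bias. The figures above show what assumed shifts would do and do not forecast this trial. The bias is smaller for a 1-week reading than for a week-4 reading if lapses are spread evenly, and nearly as large if they cluster early and all lapsers carry the shift.

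Three stronger readings go beyond the documents. The flaw does not invalidate Aim 2 as a whole, because the pre-quit piece is correctly ordered. It does not touch the Aim 1 efficacy test, which uses no mediator. It cannot be said to favour or to hide Hyp 2, because the protocol's own statements point both ways.

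This should be fixed before unblinding, because the choice among outcome models with and without smoking is otherwise left open in a primary aim.

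**What to change.** Add to the Aim 2 analysis plan:

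1. For time to lapse, base the mediation conclusion on the pre-quit piece, analysed in all randomized participants.
2. Relate post-quit pieces only to outcomes after the reading (later point prevalence abstinence), adjusted for smoking status at the reading.
3. If post-quit pieces are also related to time to lapse, treat this as a sensitivity analysis of path b only, using a landmark or a lagged time-varying mediator with timeline follow-back lapse dates. Label it as conditioning on a post-randomization event. Do not base the product-of-coefficients test on the lapse-free subset, where path a is no longer a randomized comparison.
4. Name the deciding model in advance, including whether it contains smoking as a covariate.

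No new data are needed. The cost is power for the post-quit pieces: at most about 112 of 300 would be lapse-free at week 4 on the planning rates, so a null landmark result should be reported as low-powered. Adjusting later abstinence for smoking at the reading also leaves out any mediated effect that has already acted by then.

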- 2. To test whether treatment-related enhancement of reward processing is a mechanism of action of high dose bupropion.** Hyp 2. The effects of BUP-450 vs. BUP-300 cessation outcomes will be mediated by reward processing, such that dose will predict greater improvements in reward processing, which will in turn be associated with greater odds of abstinence.

Secondary Aims

- 3. To test the effects of high dose bupropion on secondary outcomes of:** (a) anhedonia and related psychopathology (i.e., depressive, social anxiety, ADHD, PTSD symptoms), and (b) change in body weight and percent body fat composition.
- 4. To examine if baseline anhedonia level and related psychopathology (depressive, social anxiety, ADHD, PTSD symptoms) moderate the efficacy of high dose bupropion on cessation outcome.**

If successful, this research may identify a novel, highly-disseminable, cost-effective, and efficacious cessation treatment for an at-risk population, with wide-spanning implications toward offsetting three of the nation's top causes of morbidity and mortality—smoking, mental illness, and health problems due to excessive weight.

A. SIGNIFICANCE

A.1 Importance of Increasing Cessation Treatment Outcomes for Smokers Psychiatric Symptoms

While the overall population-level rate of smoking has significantly declined in recent years, smoking among those with psychiatric symptoms and conditions has remained stable,¹⁸ with SWPS accounting for a mounting proportion of the U.S. tobacco-related disease burden each year.¹ A key source of the tobacco-related health disparities facing SWPS is their disproportionately low quit rates.¹ Hence, improving smoking cessation among SPWS is vital for reducing tobacco-related disparities and counteracting the public health burden of smoking.

A.2 Current Status of Cessation Treatment Development Research for SWPS

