A recent Cochrane review found that BUP-300 mitigates the magnitude of weight gain relative to PLA and varenicline, though effects were modest and not robust at long-term follow-up.⁹⁷ Bupropion may facilitate weight loss by suppressing appetite, decreasing food reward,⁹⁸ and increasing metabolic rate via action on mesolimbic dopamine and hypothalamic melanocortin systems.⁹⁹ One of the first large trials tested the dose dependency of BUP for weight loss and showed that 400 mg/day outperformed 300 mg/day.¹⁶ Doses \geq 400mg BUP has since been the primary dose studied for weight loss, with results supporting the efficacy of BUP (vs. PLA) in various studies (2%–10% of initial body weight),^{16,17,100-103} including trials in depressed patients.¹⁰³ High dose bupropion recently garnered FDA approval for weight loss when combined with naltrexone. Because the efficacy of BUP is not dependent on a diet/behavioral weight loss intervention platform,^{16,17,100-103} **BUP-450 could prevent weight gain the smoking cessation context without weight loss counseling.** Thus, high dose bupropion may prevent post-cessation weight gain better than other cessation treatments, particularly among the population of anhedonic smokers for which weight-related health consequences are of particular concern.

A.11 Summary of the Significance of the Proposed Study

The proposed RCT of BUP-450 vs. BUP-300 aims to identify a viable method of offsetting tobacco-related health disparities facing SWPS and two other leading causes of morbidity and mortality—mental illness and excessive weight. Results will be readily translatable to real-world clinics, given the modest cost of BUP-450 and the existing prescribing practices of high dose BUP for weight loss and psychopathology. If BUP-450 does not outperform BUP-300 in quit outcomes but improves weight gain and/or mental health without additional side effects, the trial would still provide invaluable evidence of a new cessation treatment that is equally efficacious to a front line treatment (i.e., BUP-300) but has superior metabolic and/or mental health benefits.

B. INNOVATION

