relapse curves in anhedonic smokers, BUP-450 vs. BUP-300 vs. PLA effects on weight loss and mental health.^{22,97,162} We generated 1,000 multivariate normal random samples of correlated binary outcomes using covariance estimates from prior trial data (range 0.55-0.25)³ and analyzed the datasets using LGCM focusing on the proportion of significant ($p < 0.05$) values for each pair-wise contrast (Aim 1). The percentage of datasets with significant effects for each hypothesis (i.e., $>80\%$ of $ps < .05$) provided a simulation-based estimate of power. Using this technique, we found that enrolling a sample size of 375 (BUP-450: $N < 150$, BUP-300 $N < 150$) conservatively would have power >0.83 to detect main effects when testing our primary hypothesis, allowing for 20% attrition among those enrolled. Parallel simulations were conducted using LGCM to assess power for growth trajectories in continuously scaled mediators assuming an effect of treatment dose response on reward processing ($ds > 0.3$), and reward processing on outcome ($ds > 0.17$) based on the prior literature.^{131,140,201,202} We also found support for power >0.81 with average effects of 0.31 ($sd = 0.11$) with $N = 375$. Additional simulations for secondary mental health and body/weight adiposity outcomes based effects in prior literature ($ds > 0.3$)^{22,97,162} yielded adequate power ($> .80$). Missing individuals will be presumed to have continued smoking. All analyses will use an intent-to-treat approach.

REFERENCES

4. [name] AM, Zvolensky MJ. Anxiety, depression, and cigarette smoking: A transdiagnostic vulnerability framework to understanding emotion-smoking comorbidity. *Psychological bulletin*. 2015;141(1):176.
5. Gorwood P. Neurobiological mechanisms of anhedonia. *Dialogues Clin Neurosci*. 2008;10(3):291-299.

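### A.11 draws a superiority conclusion from weight and/or mental health after a null smoking result, but Aim 3 spreads these over seven outcomes with no lead, deciding contrast or error control

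*Combined protocol and SAP*

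**What the plan says.** A.11 (Summary of the Significance) considers the case where BUP-450 does not outperform BUP-300 on quitting. If it nevertheless "improves weight gain and/or mental health without additional side effects", the authors would regard the trial as evidence for a new cessation treatment, as effective as the standard dose and with metabolic and/or mental health advantages.

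The Specific Aims list the Aim 3 outcomes as "a) anhedonia and related psychopathology (i.e., depressive, social anxiety, ADHD, PTSD symptoms), and (b) change in body weight and percent body fat composition". That makes five symptom measures and two body measures. Aim 3 is labelled secondary.

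C.7 (Secondary Aims) gives the analysis: "Aim 3 will examine medication effects on anhedonia (SHAPS) and related psychopathology (i.e., depressive, social anxiety, ADHD, PTSD symptoms) and body weight", together with "body fat percentage trajectories using individual growth models (intercept and slope) of assessments at visits during treatment". Neither C.7 nor C.8 names a lead outcome, a testing order, a composite or a multiplicity adjustment for Aim 3, and neither says whether the intercept or the slope decides. The principal-component composite in C.7 concerns only the Aim 2 mediators.

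The only significance threshold is in the C.8 power simulation: "The percentage of datasets with significant effects for each hypothesis (i.e., $>80\%$ of $ps < .05". For the secondary outcomes C.8 assumes effects above d = 0.3 and reports that the simulations "yielded adequate power ($> .80".

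**The concern.** Unadjusted secondary outcomes are usually acceptable when they support a primary result. Here A.11 attaches a conclusion of its own to them for the case where the primary result is null, so no earlier significant test protects them. The conclusion is joined by and/or: a benefit in either domain is enough, one domain contains five scales and the other two measures. Nothing in the analysis plan narrows which of the seven may support it. With no true effect on any of them, the chance that something favours BUP-450 is then several times that of a single test. What is at stake is a published statement that the higher dose has superior metabolic or mental health benefits, resting on whichever outcome happened to cross 0.05.

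**Working it through.** **Inputs from the documents.** Seven outcomes (Specific Aims; C.7). Threshold 0.05 per hypothesis (C.8, power simulation only). d = 0.3 for secondary outcomes (C.8). 300 randomized 1:1, so 150 per arm (C.4, C.5). 20% attrition (C.8), which leaves 120 per arm if applied to the 300.

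**Inputs assumed.** Two-sided tests, so 0.025 in the favourable direction; 0.05 carried over to Aim 3; one test per outcome; no true effect on any outcome. Correlations are not in the documents. I use 0.3-0.6 among the five symptom scales, 0.7-0.9 between weight and body fat, and 0-0.1 across domains.

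**Step 1: the plan's own secondary power.** For a two-group comparison of means, power = Φ(d√(n/2)/√(1−r²) − 1.960), with n per arm and r the baseline correlation.
- n = 187.5 (375 in total), r = 0: Φ(2.905 − 1.960) = 0.828.
- n = 150, r = 0: Φ(2.598 − 1.960) = 0.738.
- n = 120, r = 0: Φ(2.324 − 1.960) = 0.642.
- n = 150, r = 0.5: Φ(3.000 − 1.960) = 0.851.

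The stated power above 0.80 is attainable, but C.8 does not give the N or covariances behind that sentence. These are simple approximations, not the plan's growth models.

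**Step 2: is two-sided 0.05 a fair reading?** From the C.8 abstinence rates, the log odds ratios at the four visits are 0.647, 0.609, 0.539 and 0.539, mean 0.583. With 150 per arm and correlations of 0.55, 0.40 and 0.25 at increasing lag, the standard error of that mean is about 0.199. The ratio is 2.93 and power is Φ(2.93 − 1.96) = 0.835. This agrees with the stated figure above 0.83 for the primary, so unadjusted two-sided 0.05 fits the plan's arithmetic, though the plan does not say so.

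**Step 3: chance of at least one false result favouring BUP-450.**
- One outcome: 0.025.
- Seven independent outcomes: 1 − 0.975^7 = 0.162.
- Seven correlated outcomes, by simulating multivariate normal test statistics (1,000,000 draws per case):

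| Symptom correlation | Weight/body-fat correlation | Across domains | Probability |
|---|---|---|---|
| 0.3 | 0.7 | 0 | 0.142 |
| 0.3 | 0.9 | 0.1 | 0.135 |
| 0.6 | 0.7 | 0 | 0.121 |
| 0.6 | 0.9 | 0.1 | 0.114 |

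- One common correlation among all seven: 0.103 at 0.6 and 0.074 at 0.8.
- Intercept and slope both tested (14 tests): 1 − 0.975^14 = 0.298 if independent, about 0.22 with correlation 0.5 between outcomes.

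**Step 4: effect of the fix.** With no true effects, Holm on two leads rejects something only if the smaller p-value is at most 0.025. In the favourable direction this gives 1 − (1 − 0.0125)² = 0.0248 if the leads are independent. Two leads without a split would give 1 − 0.975² = 0.049.

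**Step 5: power cost if only one lead effect is real (d = 0.3).** Replace 1.960 by 2.241.

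| n per arm | r | At 0.05 | At 0.025 |
|---|---|---|---|
| 150 | 0 | 0.738 | 0.639 |
| 120 | 0 | 0.642 | 0.533 |
| 150 | 0.5 | 0.851 | 0.776 |
| 120 | 0.5 | 0.765 | 0.671 |

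Bonferroni over all seven (0.05/7 = 0.00714) would leave 0.463 at 150 per arm with r = 0.

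**The case against.** A.11 is Significance text, not a decision rule. Success is defined by Hypothesis 1 on abstinence, and Aim 3 is openly secondary. A reader might infer that the plan offers a second route to a positive trial, or that a single significant scale can carry it. The documents do not support that. A.11 says the trial would still provide valuable evidence; it does not say the trial would be positive, or that one result in seven is enough. That objection stands.

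A.11 also requires no additional side effects, and C.7 plans side-effect comparisons. The probabilities above are therefore for at least one favourable p-value, before that condition. It can only lower the rate, but C.7 gives no criterion for meeting it, so it cannot be counted as error control.

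Two further readings should be resisted. The 16% figure is the independence limit and should not be presented as the expected value, since these outcomes are correlated. And the calculation contains no smoking outcome, so it does not give the rate conditional on a null primary.

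What remains is that A.11 states a superiority conclusion in advance, and nothing in C.7 or C.8 limits which of seven results may support it.

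**Conclusion.** The point holds as a should-fix matter about the conclusion A.11 attaches to Aim 3. It does not touch the primary test. Following the plan as written gives about an 11-14% chance of at least one false result favouring BUP-450, against 2.5% for a single outcome. This rests on two-sided 0.05, one test per outcome, no true effects and the assumed correlations. Uniformly high correlations (0.6-0.8) would bring it to about 7-10%, still roughly three to four times the single-outcome rate. Testing both growth parameters would take it to about 22-30%. The documents do not support calling this the error rate of the trial, or of the full A.11 claim with its side-effect condition.

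**What to change.** **Option 1, in C.7.** Name one lead outcome and one tested contrast per domain, for example treatment by time to the end of treatment. Without the contrast, two leads with two growth parameters each leave up to four tests, and Holm over two does not control them. SHAPS is the natural mental health lead, since anhedonia defines the target population. The sponsor should choose between body weight and percent body fat: A.11 speaks of weight gain, whereas Section B (Measurement of body fat composition outcomes) criticises weight as an index of adiposity and expects body-fat measurement to be more sensitive. Those two passages need reconciling. Test the two leads with Holm at 0.05, limit the A.11 conclusion to them, and report the other five outcomes with 95% confidence intervals as descriptive.

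**Option 2, in A.11.** State that any Aim 3 benefit after a null primary result is hypothesis-generating.

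**Cost.** Both are wording changes, with no change to design or visits. Option 1 loses roughly 0.08 to 0.11 in power when only one lead effect is real (step 5), which is less than adjusting across all seven. Option 2 costs no power but gives up the firmer conclusion.
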